5.10 End of Treatment Evaluation and Follow-Up

The End of Treatment and Follow-up visit procedures are listed in Section 9 (Study Calendar). After the end of treatment, each subject will be followed for 30 days for adverse event monitoring and 90 days for serious adverse event reporting.

Participants removed from protocol therapy for unacceptable adverse events will be following until resolution or stabilization of the adverse event.

Subjects who discontinue for reasons other than progressive disease will have post-treatment follow-up for disease status until disease progression, initiating a non-study cancer treatment, withdrawing consent or becoming lost to follow-up.

5.11 Long-Term Follow-Up and Study Completion

After documented disease progression each subject will be followed by telephone or medical record review for overall survival until they meet criteria for removal from study as detailed below.

Participants will be removed from study when any of the following criteria apply:

- Lost to follow-up
- Withdrawal of consent
- Death

The reason for taking a participant off study, and the date the participant was removed, must be documented in the case report form (CRF).

When a participant is removed from protocol therapy and/or is off of the study, the relevant Off-Treatment/Off-Study information will be updated in OnCore.

5.12 Subject Replacement Strategy

Additional subjects may be enrolled in a given Group to ensure that the required number of evaluable subjects in each cohort is achieved. A subject that discontinues the trial for progressive disease or a drug-related AE will not be replaced and will be counted in the evaluable population of subjects for the respective cohort.

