Group B: adjuvant evaluation: Fifteen eligible patients will not receive study drug prior to scheduled surgical resection for recurrent/progressive glioblastoma. The two required pre-surgical plasma samples should be drawn greater than 10 days apart - see Table 6 for full details). Tumor samples will be obtained at time of surgery. The tissue from this surgery (fresh, frozen and FFPE) and the archived tissue from the most recent surgery prior to registration revealing glioblastoma (FFPE) will be processed so as to best achieve the primary, secondary and exploratory PD objectives. After recovery from surgery (once participant has recovered from surgery, but no more than 35 days following surgery), patients will begin Q 3 week pembrolizumab at 200mg IV until tumor progression or adverse event requiring discontinuation of study drug. Blood samples will be obtained as pharmacodynamic markers throughout the study. Dose decreases and symptomatic management will occur based upon preset adverse event determination. DLTs will not be determined. The toxicity evaluation period will begin with registration and extend to 30 days after last treatment day. Patients will be followed for MRI changes, clinical exam and steroid doses from the registration period and extend to the second progression. After second progression, patients will be followed every 3 months for vital status until death.

Stage 2:

Group A expansion only: For this stage of the study, 25 additional patients will be enrolled to Group A only with a goal of 20 evaluable patients.

Expansion of Group A: Neoadjuvant/adjuvant evaluation: An additional 20-25 patients will receive a single infusion of pembrolizumab of 200mg 14± 5 days prior to scheduled surgical resection for recurrent/progressive glioblastoma (when scheduling, please keep in mind that the two pre-surgical plasma samples should be drawn greater than 10 days apart - see Table 6 for full details). Tumor samples will be obtained at time of surgery. The tissue from this surgery (fresh, frozen and FFPE) and the archived tissue from the archived tissue from the most recent surgery prior to registration revealing glioblastoma (FFPE) will be processed so as to best achieve the primary, secondary and exploratory PD objectives. After recovery from surgery (once participant has recovered from surgery, but no more than 35 days following surgery), patients will resume Q 3 week pembrolizumab at 200mg IV until tumor progression or adverse

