5.6 Patient Evaluability and Replacement

See protocol section 12.2.5 Analysis Population.

If a participant is enrolled to trial and local pathology from the on-study surgery is unable to definitively confirm recurrent tumor, then the participant will be considered non-evaluable for primary and secondary endpoints, but may continue to receive study treatment per protocol. In these instances, please contact the DFCI Coordinating Center as soon as possible to obtain Sponsor-Investigator and manufacturer approval.

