12.2.3 Power and Sample Size for primary endpoint

Stage 1:

Group B is an independent concurrent control to evaluate TIL density in Group A due to the infeasibility of multiple resections within a short time period for patients with recurrent GBM. Patients will be randomly assigned to either group A or B with a 1:1 randomization ratio prior to surgery. Based on our preliminary data, the mean of TIL density is estimated to be 0.4 (T cell per nucleating) (SD = 0.5) in the control group (Group B). Fifteen patients per group (total of 30 evaluable) achieve 85% power to detect an increase of 0.5 of TIL density comparing Group A versus Group B at an alpha level of 0.05 (1-sided) using a two-sample t-test.

Stage 2:

An extension based on interim data has the primary scientific endpoint of evaluating the cell cycle signature in patients receiving neoadjuvant pembrolizumab. This extension will aim to enroll 25 additional patients with a goal of 20 evaluable patients to Group A. Group B is an independent

concurrent control to evaluate the cell cycle-related gene signature in Group A. Based on the preliminary data, the mean tumor cell cycle-related gene expression signature is estimated to be -0.3 for neoadjuvant pembrolizumab (SD=0.66) and +0.37 for control (SD=0.64), which corresponds to an effect size of 1.1. With the addition of 20 more patients in Group A, the one-sided two-sample T-test (alpha level: 0.05) will have 81.73% power to detect an effect size of 1.1 for the difference of tumor cell cycle-related gene expression signature between the two groups.

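### Section 5.12 counts patients as evaluable by a clinical-endpoint rule, so the targets set for the tissue-based primary tests can be filled by patients who never provide tumour tissue

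*Combined protocol and SAP*

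**What the plan says.** Section 5.12 allows extra enrolment to reach the required evaluable number, then makes an exception: a subject who stops for progression or a drug-related adverse event "will not be replaced and will be counted in the evaluable population of subjects for the respective cohort". It does not ask whether surgery took place or a specimen exists.

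The targets it serves are in 12.2.3 and section 5. For Stage 1: "Fifteen patients per group (total of 30 evaluable) achieve 85% power to detect an increase of 0.5 of TIL density", "at an alpha level of 0.05 (1-sided) using a two-sample t-test". For Stage 2: "25 additional patients will be enrolled to Group A only with a goal of 20 evaluable patients". The endpoints are TIL density (Stage 1) and the cell-cycle signature by RNA sequencing (Stage 2). Sections 5, 8.2 and 8.4 and Table 6 take both from tumour removed at the protocol surgery.

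Three other places bear on evaluability:

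- Section 5.6 applies when local pathology on the protocol-surgery specimen is "unable to definitively confirm recurrent tumor, then the participant will be considered non-evaluable for primary and secondary endpoints". Otherwise it points to 12.2.5.
- Section 12.2.5 defines the FAS by receipt of one dose, FAS-2 by a post-baseline scan or by stopping for progression or a drug-related event, and ITT by randomisation. None requires tissue.
- Section 5.8.1 refers to evaluability for tumour tissue studies and leaves it to confirmation by the overall principal investigator. No section defines it.

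**The concern.** The 5.12 rule suits a clinical endpoint: a patient who stops for progression or toxicity has had an outcome and should not be swapped for a healthier one. A t-test on tissue is different, because a patient without a specimen contributes nothing to it.

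Group A receives its neoadjuvant dose 14 ± 5 days before surgery, that is, 9 to 19 days. A patient who stops for one of the two named reasons in that interval and is not resected is counted as evaluable, is not replaced and has no value for the primary test. Section 5.6 does not reach this patient, because it presupposes an operation. Nor does 12.2.5: a dosed but unresected Group A patient is in the FAS, while a Group B patient who gave tissue but never started drug is not.

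Two things are at stake. Accrual can close at 20 evaluable patients with fewer than 20 assay results, while some of the 25 planned places go unused. And the missing specimens would come from patients with early toxicity or early deterioration, which could make the group comparison selective. Section 12.2.7 asks for reasons for discontinuation but not for losses of tissue.

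**Working it through.** **Inputs.** Stage 1 (12.2.3): difference 0.5, SD 0.5, so d = 0.5/0.5 = 1.0; 15 per group; one-sided alpha 0.05. Stage 2 (12.2.3): d = 1.1, one-sided alpha 0.05, 20 more patients in Group A. The number of patients lost before surgery is not in the documents. I take k = 0 to 5 Group A samples as an assumed range; five equals the planned Stage 2 allowance, 25 − 20.

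**Formula.** Power = P(T > t₀.₉₅,df), where T is noncentral t with df = nA + nB − 2 and noncentrality d/√(1/nA + 1/nB).

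**The plan's Stage 1 figure.** For 15 v 15 the noncentrality is 1/√(2/15) = 2.74 with 28 df. Power is 84.8%, which reproduces the stated 85%.

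**Stage 1 with k Group A samples missing, Group B at 15:**

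| k | nA v nB | Power |
|---|---|---|
| 0 | 15 v 15 | 84.8% |
| 1 | 14 v 15 | 83.6% |
| 2 | 13 v 15 | 82.2% |
| 3 | 12 v 15 | 80.7% |
| 4 | 11 v 15 | 78.9% |
| 5 | 10 v 15 | 76.8% |

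Each missing sample costs about 1.2 to 2.1 points. Power falls below 80% at the fourth.

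**Stage 2.** Section 12.2.3 does not say how many Stage 1 samples from either group enter the test, so I show several cases. Pooled, Group A is 15 + 20 = 35. The rows with 8 in Group B are an assumption, used only to show the effect of a smaller control group.

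| Case | k = 0 | k = 5 | Loss (points) |
|---|---|---|---|
| Pooled, Group B 15 | 35 v 15: 96.9% | 30 v 15: 96.2% | 0.7 |
| Pooled, Group B 8 (assumed) | 35 v 8: 86.8% | 30 v 8: 85.7% | 1.1 |
| Not pooled, Group B 15 | 20 v 15: 93.4% | 15 v 15: 90.2% | 3.2 |
| Not pooled, Group B 8 (assumed) | 20 v 8: 82.0% | 15 v 8: 78.4% | 3.6 |

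The plan's Stage 2 figure of 81.73% is not reproduced by 35 v 15 or 20 v 15. That is a separate matter, but it means the base from which these losses should be subtracted is uncertain.

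**Which losses count.** Four conditions must hold together: the patient is enrolled, stops for progression or a drug-related event, does so before surgery, and is not resected. The drug-related limb can meet them only in Group A, because Group B has no drug before surgery. The progression limb can meet them in either group.

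**The case against.** The trigger is narrow. Criterion 3.1.16 requires the surgery to be clinically indicated, so stopping drug need not cancel it. Patients who stop after surgery have already given tissue and are rightly counted. Progression before surgery would mostly mean clinical deterioration, since the screening scan is not used for response (3.1.9) and on-study scans are tied to the post-surgical cycles. All of this stands, and it limits the point to a small number of patients.

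Stage 1 also looks closed. Section 1.1 reports 35 patients enrolled by September 2017 against a target of 30 evaluable, and the synopsis gives remaining time for Stage 2 only. The documents do not say how many of the 35 yielded usable tissue, but the Stage 1 table is now largely retrospective.

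It can also be said that evaluability is meant to be endpoint-specific: the 5.12 wording resembles FAS-2, 5.6 speaks to primary and secondary endpoints, and 5.8.1 treats tissue evaluability separately. That is a fair reading of intent. It does not settle which count closes accrual, because 5.12 names only one evaluable population and no section defines the other.

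Two stronger readings are not supported. A reader might infer that the whole shortfall falls on Group A; the progression limb reaches Group B too. A reader might also infer that adding subjects to a given group lets Stage 1 places be filled outside the randomisation. The phrase does not waive the rule in 12.2.3: "Patients will be randomly assigned to either group A or B with a 1:1 randomization ratio prior to surgery".

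**Conclusion.** The point holds in a limited form. Section 5.12 attaches a clinical-endpoint rule to targets that were calculated for tissue tests, and neither 5.6 nor 12.2.5 covers a patient who never reaches surgery. Applied as written, it can close Stage 2 at 20 evaluable patients with fewer than 20 new assay results.

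The likely cost in power is modest. For five lost Group A samples in Stage 2 it is about 1 point with pooling and about 3 to 4 points without, given d = 1.1 and the Group B counts shown. A reader might infer from the 76.8% in the Stage 1 table that the trial is materially underpowered. The documents do not support that: the figure assumes that a third of Group A (5 of 15) gave no tissue, and no loss rate is stated. The possibility of selective loss is real, but its size cannot be estimated from the documents. The reason to act is that the correction is cheap and fits within enrolment already planned.

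**What to change.** In 5.12, with cross-references in 5.6 and 12.2.3:

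1. Define evaluable for the primary tissue endpoint as on-study surgery done, tumour confirmed and assay result available.
2. Count the Stage 2 goal of 20 on that definition, and replace patients without tissue, whatever the reason, within the 25 already planned. If 25 are enrolled and fewer than 20 have results, report the shortfall.
3. Limit the existing no-replacement rule to the clinical and safety endpoints.
4. Keep patients without tissue in whichever of the safety, FAS and ITT sets they qualify for under 12.2.5. This must be checked set by set: an undosed Group B patient is in neither the FAS nor the safety set, and Stage 2 patients are not randomised and so are outside ITT as defined.
5. Report the number of patients without tissue, and the reason, by group. Replacement restores the sample count but does not remove selection caused by early losses.

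The cost is a few sentences of text and one table. It needs no enrolment beyond the 25 and no change to any treatment rule.

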5.13 Beginning and End of the Trial

The study begins when the first subject signs the informed consent (either pre-screening consent or main study consent). The end of the study may be designated as the time point when all subjects have discontinued the study or are a minimum of 6 months post initial study medication administration. If, by the end of the study, there remains at least 1 subject still on study treatment for at least 6 months, the subject(s) may enter additional treatment cycles.

The subject is considered on study until such time that he/she meets any of the discontinuation criteria and notification is given to the Sponsor.

6. ADVERSE EVENTS: LIST AND REPORTING REQUIREMENTS

An adverse event is defined as any untoward medical occurrence in a patient or clinical investigation subject administered a pharmaceutical product and which does not necessarily have to have a causal relationship with this treatment. An adverse event can therefore be any unfavorable and unintended sign (including an abnormal laboratory finding, for example), symptom, or disease temporally associated with the use of a medicinal product or protocol-specified procedure, whether or not considered related to the medicinal product or protocol-specified procedure. Any worsening (i.e., any clinically significant adverse change in frequency and/or intensity) of a preexisting condition that is temporally associated with the use of the Merck's product, is also an adverse event.

Changes resulting from normal growth and development that do not vary significantly in frequency or severity from expected levels are not to be considered adverse events. Examples of this may include, but are not limited to onset of menses or menopause occurring at a physiologically appropriate time.

Merck product includes any pharmaceutical product, biological product, device, diagnostic agent or protocol-specified procedure, whether investigational (including placebo or active comparator medication) or marketed, manufactured by, licensed by, provided by or distributed by Merck for human use.

Adverse events may occur during the course of the use of Merck product in clinical trials or within the follow-up period specified by the protocol, or prescribed in clinical practice, from overdose (whether accidental or intentional), from abuse and from withdrawal.

Adverse events may also occur in screened subjects during any pre-allocation baseline period as a

result of a protocol-specified intervention, including washout or discontinuation of usual therapy, diet, placebo treatment or a procedure.

Progression of the cancer under study is not considered an adverse event.

All adverse events will be recorded from registration through 30 days following cessation of treatment and at each examination on the Adverse Event case report forms/worksheets. The reporting timeframe for adverse events meeting any serious criteria is described in section 6.3.

Adverse events will not be collected for subjects during the pre-screening period (for determination of archival tissue status) as long as that subject has not undergone any protocol-specified procedure or intervention. If the subject requires a blood draw, fresh tumor biopsy etc., the subject is first required to provide consent to the main study and AEs will be captured according to guidelines for standard AE reporting.

6.1 Definition of an Overdose for This Protocol and Reporting of Overdose to the Sponsor and to Merck

For purposes of this trial, an overdose of pembrolizumab will be defined as any dose of 1,000 mg or greater (≥ 5 times the indicated dose). No specific information is available on the treatment of overdose of pembrolizumab. Appropriate supportive treatment should be provided if clinically indicated. In the event of overdose, the subject should be observed closely for signs of toxicity. Appropriate supportive treatment should be provided if clinically indicated.

If an adverse event(s) is associated with (“results from”) the overdose of a Merck product, the adverse event(s) is reported as a serious adverse event, even if no other seriousness criteria are met.

If a dose of Merck’s product meeting the protocol definition of overdose is taken without any associated clinical symptoms or abnormal laboratory results, the overdose is reported as a non-serious Event of Clinical Interest (ECI), using the terminology “accidental or intentional overdose without adverse effect.”

All reports of overdose with and without an adverse event must be reported within 1 working day hours to the DFCI Coordinating Center and Overall PI ([name]) and within 2 working days hours (see Appendix C DFCI Reportable AE Coversheet) to Merck Global Safety (Attn: Worldwide Product Safety; [contact]). The DFCI Neuro-Oncology Coordinating Center central SAE email should be copied on the submission ([contact]).

6.2 Reporting of Pregnancy and Lactation to the Sponsor and to Merck

Although pregnancy and lactation are not considered adverse events, it is the responsibility of investigators or their designees to report any pregnancy or lactation in a subject (spontaneously reported to them) that occurs during the trial.

Pregnancies and lactations that occur after the consent form is signed but before treatment

allocation/randomization must be reported by the investigator if they cause the subject to be excluded from the trial, or are the result of a protocol-specified intervention, including but not limited to washout or discontinuation of usual therapy, diet, placebo treatment or a procedure.

Pregnancies and lactations that occur from the time of treatment allocation/randomization through 120 days following cessation of Sponsor's product, or 30 days following cessation of treatment if the subject initiates new anticancer therapy, whichever is earlier, must be reported by the investigator. All reported pregnancies must be followed to the completion/termination of the pregnancy. Pregnancy outcomes of spontaneous abortion, missed abortion, benign hydatidiform mole, blighted ovum, fetal death, intrauterine death, miscarriage and stillbirth must be reported as serious events (Important Medical Events). If the pregnancy continues to term, the outcome (health of infant) must also be reported.

Such events must be reported within 1 working day to the DFCI Coordinating Center and Overall PI ([name] – see Appendix C DFCI Reportable AE Coversheet) and within 2 working days to Merck Global Safety (Attn: Worldwide Product Safety; [contact]). The DFCI Neuro Oncology Coordinating Center central SAE email should be copied on the submission ([contact]).

6.3 Immediate Reporting of Adverse Events to the Sponsor and to Merck

6.3.1 Serious Adverse Events

A serious adverse event is any adverse event occurring at any dose or during any use of Merck's product that:

- Results in death;
- Is life threatening;
- Results in persistent or significant disability/incapacity;
- Results in or prolongs an existing inpatient hospitalization;
- Is a congenital anomaly/birth defect;
- Is a new cancer (that is not a condition of the study);
- Is associated with an overdose;
- Is another important medical event

Refer to Table 5 for additional details regarding each of the above criteria.

Progression of the cancer under study is not considered an adverse event unless it results in hospitalization or death. See section 6.3.1.5 Protocol Specific Expedited Adverse Event Reporting Exclusions for other events not requiring expedited reporting.

Any serious adverse event, or follow up to a serious adverse event, including death due to any cause other than progression of the cancer under study that occurs to any subject from the time the consent is signed through 90 days following cessation of treatment, or the initiation of new anti-cancer therapy, whichever is earlier, whether or not related to Merck product, must be reported within 1 working day to the DFCI Coordinating Center (see Appendix C DFCI Reportable AE Coversheet) and Overall PI and within 2 working days to Merck Global Safety.

Non-serious Events of Clinical Interest will be forwarded to Merck Global Safety and will be handled in the same manner as SAEs.

Additionally, any serious adverse event, considered by an investigator who is a qualified physician to be related to Merck product that is brought to the attention of the investigator at any time outside of the time period specified in the previous paragraph also must be reported immediately to the DFCI Coordinating Center, Overall PI and to Merck.

SAE reports and any other relevant safety information are to be forwarded to the Merck Global Safety [contact]

A copy of all 15 Day Reports and Annual Progress Reports is submitted as required by FDA, European Union (EU), Pharmaceutical and Medical Devices agency (PMDA) or other local regulators. Investigators will cross reference this submission according to local regulations to the Merck Investigational Compound Number (IND, CSA, etc.) at the time of submission. Additionally investigators will submit a copy of these reports to Merck & Co., Inc. (Attn: Worldwide Product Safety; [contact]) at the time of submission to FDA.

All subjects with serious adverse events must be followed up for outcome.

Investigators **must** report to the Overall PI any serious adverse event (SAE) that occurs after the initial dose of study treatment, during treatment, or within 90 days of the last dose of treatment (or the initiation of new anti-cancer therapy, whichever is earlier) on the local institutional SAE form.

For multi-institution studies where a DF/HCC investigator is serving as the Overall Principal Investigator, each participating institution **must** abide by the reporting requirements set by the DF/HCC. This applies to any medical event equivalent to an unexpected grade 2 or 3 with a possible, probable or definite attribution, unexpected grade 4 toxicities, and grade 5 (death) regardless of study phase or attribution.

